20. DATA ANALYSIS PLAN

The molecular genetic analysis will be centered on assays of genomic variability including large-scale genotyping or whole genome sequencing of risk variants and disease-linked mutation detection. Psomagen, Inc., a MJFF-contracted gene sequencing center(s) and biorepository will not receive any personal identifiable information that would link the samples back to individual study participants. The outcome of this study is to identify genomic variability that causes or modulates risk for PD.

Control data may be obtained in part from publicly available resources to match PD cases based on genetic background when individual genetic data exists.

To explore genetic risk factors associated with PD in this population, logistic regression, score and fisher exact tests will be used to test each of the imputed variants for an association with disease, adjusting for population substructure, age and gender. From this analysis, PD loci of interest will be extracted to compare with known local risk estimates in other populations. To study the influence of genetic variation on disease onset, linear regression will be applied adjusting by similar covariates. Subsequently, cumulative risk score will be evaluated by selecting the 90 risk loci conferring risk for PD in the European population. SNPs will be weighted by their log odds ratios (as per Nalls et al., 2019), giving greater weight to alleles with higher risk estimates, and a composite genetic risk score will be generated across all risk loci. Genetic risk score will be z-transformed prior to analysis, centered on controls, with a mean of zero and a standard deviation of one in the control participants. Regression models will then be applied to test for association with the risk of developing PD (based on logistic regression) or age at onset, and disease duration (linear regression), adjusting for sex, age, and principal components to account for population stratification. These analyses will be performed using PLINK 1.9 and R.

Additionally, in an effort of studying the proportion of the phenotype attributable to genetic influence, heritability estimates will be calculated. If disease heritability estimates are similar than those in European populations, that could corroborate the lower incidence of PD within this population, probably only explained by health disparities in PD diagnosis. The narrow-sense heritability (h2), a measure of the additive genetic variance, will be calculated using GREML-LDMS to determine how much of the genetic liability for PD is explained by common genetic variants. This analysis will be adjusted for sex, age, and principal components to account for ascertainment bias. To estimate the influence of rare genetic variation on PD etiology, genome-wide gene-based sequence kernel association test - optimized (SKAT-O) analysis of missense and loss-of-function mutations will be performed to determine the difference in the aggregate burden of rare coding variants between

RSRB Study Number: 00006240

Page 21 of 24 Version 5.0

PD cases and controls. This analysis will be performed using RVTESTS. Finally, fast-structure analyses will be performed in order to conduct a pilot trans-ethnic fine-mapping study. Additional analyses may include: runs of homozygosity to further study families with recessive patterns of inheritance, copy number variation and machine learning pipelines.

To evaluate impaired olfactory function in Parkinson's disease patients of African admixed ancestry, we will conduct statistical analyses using SIT scores (Smell Identification Test), a standardized test used to assess a person's ability to identify different odors. The total score is the sum of correct identifications across all odor strips in the test, containing a 40-item scratch and sniff test. When analyzing SIT scores in the context of Parkinson's disease, a lower score on the test may indicate impaired olfactory function. In the case of Parkinson's disease, the loss of smell often occurs before the onset of motor symptoms, making olfactory testing a potential tool for early detection.

From the statistical standpoint, we will explore whether the SIT score is predictive of Parkinson's status in the African admixed population by running a logistic regression analysis, specifying Parkinson's status as the outcome and SIT score as the primary predictive variable of interest. SIT scores will first be normalized to the control mean and standard deviation for the relevant reference population. This helps contextualize the results on to an interpretable scale across populations and place the results in context to understand how an individual's score compares to the general population in terms of standard deviations of change. We will conduct a logistic regression adjusted by gender, age, and principal components to account for population stratification (also on a similar normalized scale). In a stepwise manner, we will prune the initial model to build a more parsimonious model. Finally, we will evaluate the overall fit of the model(s) using metrics like AUC, balanced accuracy and pseudo-R-squared to evaluate the predictive strength of the model(s).

When analyzing SIT scores in the context of PD, a lower score on the test may indicate impaired olfactory function. Olfactory function may be designated as abnormal based on available normative data for age and sex (Brumm, 2023; Doty, 1984). However, the samples on which normative data were generated lack diversity. Smell test data collected from healthy controls in BLAAC PD will be leveraged to improve generalizability of existing normative data to the Black and African American community. From the statistical standpoint, we explore whether the SIT score is predictive of PD status in the African admixed population by running a logistic regression analysis, specifying PD status as the outcome and SIT score as the primary predictive variable of interest. We will conduct logistic regression adjusted by sex, age, and PCs to account for population stratification (on a normalized scale). In a stepwise manner, we will prune the initial model to build a more parsimonious model. Finally, we evaluate the overall fit of the model(s) using metrics like AUC, balanced accuracy and pseudo-R-squared to evaluate the predictive strength of the model(s).

Finally, study methods and collected phenotypic data may be the basis of additional analysis to report on learnings around engagement of Black and African Americans in genetic Parkinson's research. Potential investigation could focus on, for example, outreach methods, enrollment or declination motivations, and study cohort demographics. These findings may inform future research engagement methods and study design for projects partnering with the Black and African American community.

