| | The Specific Aims of this study are: Screening of pathogenic variants present in the NeuroBooster (previously NeuroPlus) Array Genotyping Platform and analysis of their frequencies in the African or African admixed population. Genome-wide assessment involving cumulative risk score calculation versus disease status and age at onset and comparison with European populations and heritability calculation. Pilot analysis of trans-ethnic fine-mapping and admixture mapping to establish analysis pipelines for future larger studies. Conduct genetic-phenotypic correlations to understand the relationship between genetic variation and observable clinical traits (like dementia) in these populations Develop and systematically test strategies that enable recruitment of Black Americans and African Americans to participate in PD genetics research | |
| Study Population | Black Americans and African Americans with Parkinson's Disease or without a history of parkinsonism (control participants). | |
| Study Design | This is a multi-center observational study. | |
| Number of Participants | Up to 2,000 participants with Parkinson's Disease (PD) and up to 2,000 healthy | |
| | controls self-identifying as Black and/or African American. | |
| Inclusion Criteria | Inclusion Criteria for Participants with Parkinson's disease: | |
| | Willing and able to provide informed consent or have a legally authorized representative to provide consent | |
| | Willing and able to complete all study activities | |
| | Age 18 years or older | |
| | Self-identify as Black or African American | |
| | Meet the Movement Disorder Society's diagnostic criteria for Parkinson's disease | |
| | English speaking | |

RSRB Study Number: 00006240

Page 5 of 24 Version 5.0

| | Inclusion Criteria for Control Participants: Willing and able to provide informed consent or have a legally authorized representative to provide consent Willing and able to complete all study activities Age 18 years or older Self-identify as Black or African American English speaking | |
|-------------------------------|---|--|
| Exclusion Criteria | Exclusion Criteria for Participants with Parkinson's disease: | |

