| | Exclusion Criteria for Control Participants: Diagnosis of the following disorders: Parkinson's disease, Alzheimer's disease, Frontotemporal dementia, Corticobasal syndrome, Dementia with Lewy bodies, Motor neuron disease, Multiple system atrophy, Progressive supranuclear palsy, Spinocerebellar Ataxia (SCA), REM sleep behavior disorder, Any other parkinsonian disorder or dementia NOS Familial history of any of the following disorders in a 1st degree relative (participant's parent, sibling or child): Parkinson's disease, Alzheimer's disease, Frontotemporal dementia, Corticobasal syndrome, Dementia with Lewy bodies, Motor neuron disease, Multiple system atrophy, Progressive supranuclear palsy, Spinocerebellar Ataxia (SCA), REM sleep behavior disorder, Any other parkinsonian disorder or dementia NOS Any condition that, in the investigator's opinion, precludes the individual's ability to carry out study activities | |
| Primary Outcome Measures | Novel risk factors and characterization of known genetic risk factors contributing to PD risk in the Black or African American population. | |
| Sample Size Considerations | The study aims to recruit up to 2000 participants with PD and up to 2,000 controls. Power calculations were performed using the GAS power calculation tool by Abecasis et al. Our power to detect an association between common genetic variation (minor allele frequency < 5%) and PD risk was estimated to be 99.8% considering a general disease prevalence = 0.1% (Tysnes et al 2017) and a genotype relative risk effect = 1.5 when including 2,000 cases and 2,000 controls at a significance p-value < 5×10-8 assuming the limitation that the genetic architecture in the Black and/or African American ancestry is unknown. | |

BLAAC PD SCHEDULE OF ACTIVITIES

| Activity | Cases | Controls |
|-----------------------|-------|----------|
| Informed Consent | х | Х |
| Participant ID Number | х | Х |
| Demographics | Х | х |
| Inclusion/Exclusion | х | Х |

RSRB Study Number: 00006240

Page 6 of 24 Version 5.0

| Activity | Cases | Controls |
|--------------------------------------|-------|----------|
| Recruitment source questionnaire | X | Х |
| Family history questionnaire | х | Х |
| PD Features | х | |
| CISI-PD | х | |
| REM sleep behavior disorder question | х | Х |
| MDS UPDRS item 1.12 | х | Х |
| Environmental exposure questionnaire | х | Х |
| Montreal Cognitive Assessment | х | Х |
| Reportable Events | х | Х |
| Biosample Collection | х | Х |

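### Fisher's exact test is listed among the ancestry-adjusted single-variant tests, but it cannot carry the stated adjustment and can mislead if cases and controls differ in ancestry

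*Protocol*

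**What the plan says.** Section 20 (Data Analysis Plan) names logistic regression first and then says that "score and fisher exact tests will be used to test each of the imputed variants for an association with disease, adjusting for population substructure". In full, the adjustment clause reads "adjusting for population substructure, age and gender". The adjustment clause covers all three tests. The section does not restrict Fisher's test to sparse variants, to strata or to a supporting role.

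The next sentence uses the results to choose loci: "From this analysis, PD loci of interest will be extracted to compare with known local risk estimates in other populations". For the risk-score regressions later in the section, the device is explicit: "adjusting for sex, age, and principal components to account for population stratification".

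Three other statements bear on the point. In the Synopsis, the first specific aim describes the population of interest through "analysis of their frequencies in the African or African admixed population". Section 20 says "Control data may be obtained in part from publicly available resources to match PD cases based on genetic background". The Synopsis power statement refers to detection "when including 2,000 cases and 2,000 controls at a significance p-value < 5×10-8".

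**The concern.** Fisher's exact test conditions on the margins of a single count table. It has no place for age, for sex or for a continuous measure of ancestry such as a principal component. A stratified exact test would be possible, but it needs discrete strata and the protocol defines none. One of the three named tests therefore cannot deliver what the sentence promises. This is an error in what the text says, not a detail deferred to a statistical analysis plan.

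The stake is confounding by ancestry. In an admixed population, a variant unrelated to PD will differ in frequency between cases and controls if two things hold together: the groups differ in mean ancestry, and the variant's frequency differs between the ancestral populations. An unadjusted test reads that difference as association. Loci are taken forward from this set of tests and the primary outcome includes novel risk factors, so an unadjusted p-value has a possible route into the main results.

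**Working it through.** The protocol gives no false-positive rate for the single-variant tests, so there is no figure of its own to reproduce here. Its power figure concerns a different quantity, and this point does not depend on it.

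**Inputs from the protocol:** 2,000 cases and 2,000 controls and the 5×10⁻⁸ level (Synopsis, power statement); a minimum of 1,000 per group (Section 3).

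**Inputs assumed, because the documents do not give them:** allele frequency 0.2 on African-ancestry chromosomes; mean European ancestry 20% in the reference group; a case-control difference in mean ancestry D of 0, 3 or 5 percentage points; a frequency difference d between ancestral populations of 0.2, 0.4 or 0.6; two-sided testing.

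**Formula.** With no true effect, the expected case-control difference in allele frequency is D × d. With N people, hence 2N alleles, per group and p = 0.2 + 0.2d, the shift in the test statistic is

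z = D × d / √(2p(1 − p)/2N).

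The rejection rate is the two-sided normal tail probability given that shift. The critical value is 1.96 at 0.05 and 5.45 at 5×10⁻⁸.

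**Worked cell, D = 0.05, d = 0.6, N = 2,000:** p = 0.2 + 0.2 × 0.6 = 0.32. The standard error is √(2 × 0.32 × 0.68/4,000) = 0.01043. So z = 0.03/0.01043 = 2.88, which gives 82% at 0.05 and about 0.5% at 5×10⁻⁸.

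| D | d | z | Rejection at 0.05 | Rejection at 5×10⁻⁸ |
|---|---|---|---|---|
| 0 | any | 0 | 5% | 5×10⁻⁸ |
| 3 points | 0.2 | 0.63 | 10% | 7×10⁻⁷ |
| 3 points | 0.4 | 1.19 | 22% | 1×10⁻⁵ |
| 3 points | 0.6 | 1.73 | 41% | 1×10⁻⁴ |
| 5 points | 0.2 | 1.05 | 18% | 5×10⁻⁶ |
| 5 points | 0.4 | 1.99 | 51% | 3×10⁻⁴ |
| 5 points | 0.6 | 2.88 | 82% | 5×10⁻³ |

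At the minimum of 1,000 per group, the largest cell falls to z = 2.03, which is 53% at 0.05 and about 0.03% at 5×10⁻⁸.

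**Simulation check under separate assumptions.** Data with no true effect were generated for 2,000 v 2,000, with mean African ancestry 0.80 in controls, ancestry SD 0.10, European-ancestry allele frequency 0.2, and 600 replicates in each of 16 scenarios. Logistic regression carried individual ancestry as a covariate.

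- D = 0: Fisher's test rejected in 4.2% to 5.5% at 0.05, so there was no inflation.
- d = 0: Fisher's test rejected in 4.2% to 6.0%, whatever the ancestry difference.
- D = 2 points: 9.5%, 14.3% and 28.0% for d = 0.3, 0.5 and 0.7.
- D = 5 points: 25.5%, 62.3% and 95.3% for the same d; at 5×10⁻⁸ with d = 0.7, 2.5%.
- Adjusted logistic regression: 2.7% to 6.5% across all 16 scenarios (Monte Carlo standard error about 0.9 points), with no rejection at 5×10⁻⁸.

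Both conditions are needed for inflation, and adjustment for ancestry removes it.

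**The case against.** The strongest defence is that two valid, adjustable tests stand in the same sentence. A Fisher signal would sit beside an adjusted result for the same variant, and the risk-score, heritability and smell-test analyses all adjust for principal components. That stands. The defect is an extra, invalid route to a signal, not the absence of a valid one.

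A reader might infer more than the documents support:

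- **That an admixed sample by itself produces false associations.** It does not. An ancestry difference between cases and controls is also needed, and the documents report none.
- **That the recruitment plan builds in such a difference.** Section 5 recruits people with and without PD through one shared list of channels. Public controls are mentioned in order to match cases on genetic background. That wording is permissive and says nothing about the study's own controls, so a difference is possible but not shown.
- **That a Fisher p-value below 5×10⁻⁸ would be declared a hit.** That level appears only in the power statement. Section 20 attaches no threshold to any of the tests, and how discordant results are resolved may properly sit in a statistical analysis plan.
- **That many false loci should be expected.** The largest cell in the table would give about 25 false signals among the roughly 5,000 ancestry-informative markers (5,000 × 0.005), but only if every one differed by 0.6. With a 3-point ancestry difference the same calculation gives about 0.5, and at 1,000 per group the largest cell gives about 1.6. Section 2 introduces those markers for local-ancestry methods, not for this test.
- **That imputed variants rule out Fisher's test.** It needs counts, but the protocol does not exclude converting imputed genotypes to hard calls.

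**Conclusion.** The sentence is wrong as written: it attaches an adjustment for substructure, age and gender to a test that cannot carry one. The consequence is conditional. Fisher's p-values can be inflated for ancestry-differentiated variants if cases and controls differ in mean ancestry, and not otherwise.

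Over the tabulated range, the unadjusted test rejects in about 10% to 82% at nominal 0.05. At 5×10⁻⁸ the rate is many times nominal but small in absolute terms, at most about 0.5%. These sizes rest on assumed ancestry and allele-frequency values and would change with them. The error in the text does not depend on them. It deserves correction because the results select loci and the valid alternative is already named.

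**What to change.** In Section 20, state that association claims and the extraction of loci rest on the covariate-adjusted logistic regression or score test, with sex, age and ancestry principal components as covariates. For sparse variants, where an exact test might otherwise be wanted, use a method that takes the same covariates, such as Firth-penalised logistic regression or a saddlepoint-corrected score test. Either drop Fisher's exact test or label it unadjusted and descriptive, so that it cannot nominate a locus by itself. Removing it is not essential if it is labelled in that way.

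The cost is a change of wording before analysis and slightly more computing with standard software. No change to recruitment, sample size or data collection is needed.

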4. INCLUSION AND EXCLUSION CRITERIA

Inclusion Criteria for Participants with Parkinson's disease:

- Able and willing to provide informed consent or have a legally authorized representative to provide consent
- Age 18 or older
- English speaking
- Self-identify as Black or African American
- Meet the Movement Disorder Society's diagnostic criteria for Parkinson's disease

Exclusion Criteria for Participants with Parkinson's disease:

 Any condition that, in the investigator's opinion, precludes the individual's ability to carry out study activities

Inclusion Criteria for Control Participants:

 Able and willing to provide informed consent or have a legally authorized representative to provide consent

RSRB Study Number: 00006240

Page 10 of 24 Version 5.0

- Willing and able to complete all study activities
- Age 18 years or older
- English speaking
- Self-identify as Black or African American

Exclusion Criteria for Control Participants:

- Diagnosis of Parkinson's disease and/or any of the following disorders: Alzheimer's disease, Frontotemporal dementia, Corticobasal syndrome, Dementia with Lewy bodies, Motor neuron disease, Multiple system atrophy, Progressive supranuclear palsy, Spinocerebellar Ataxia, REM sleep behavior disorder, or any other parkinsonian disorder or dementia NOS
- Familial history of PD and/or any of the following disorders: Alzheimer's disease,
 Frontotemporal dementia, Corticobasal syndrome, Dementia with Lewy bodies, Motor neuron disease, Multiple system atrophy, Progressive supranuclear palsy, Spinocerebellar Ataxia, REM sleep behavior disorder, or any other parkinsonian disorder or dementia NOS
- Any other condition that, in the investigator's opinion, precludes the individual's ability to carry out study activities

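### The heritability comparison cannot explain why PD incidence is lower, and sex, age and principal components do not correct case-control ascertainment

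*Protocol*

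**What the plan says.** All of the disputed wording is in Protocol Section 20 (Data Analysis Plan), in the paragraph on heritability.

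- **Interpretation.** "If disease heritability estimates are similar than those in European populations, that could corroborate the lower incidence of PD within this population", a lower incidence that the text then describes as "probably only explained by health disparities in PD diagnosis".
- **Target and estimator.** Narrow-sense heritability "will be calculated using GREML-LDMS to determine how much of the genetic liability for PD is explained by common genetic variants".
- **Covariates.** "This analysis will be adjusted for sex, age, and principal components to account for ascertainment bias".

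Elsewhere in Section 20 the same covariates have a different job. The risk-score regressions are run "adjusting for sex, age, and principal components to account for population stratification", and the smell-test regressions give the same reason.

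The sampling is described in several places:

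- The Synopsis (Sample Size Considerations) says "The study aims to recruit up to 2000 participants with PD and up to 2,000 controls". Its power calculation is made "considering a general disease prevalence = 0.1" per cent. That is the only prevalence in the protocol, and it is not tied to the heritability analysis.
- Section 3 includes familial as well as sporadic cases.
- Section 4 excludes controls with "Familial history of PD and/or any of the following disorders: Alzheimer's disease" and other listed conditions.
- Section 20 allows some control data to come from public resources.

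**The concern.** There are two separate problems, and both are in what the protocol states.

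**The inference.** Incidence depends on where a population's mean liability lies relative to the disease threshold, and on how many true cases are found. Heritability describes how variation within that population divides into genetic and other parts. Similar heritability in two populations is compatible with truly lower incidence in one of them, with under-diagnosis, or with both. Every recruited case already meets the diagnostic criteria, and no planned analysis measures incidence or the rate of missed diagnosis.

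**The covariates.** Ascertainment here arises because cases are about half of the sample and a tiny fraction of the population, and because family history affects selection. Regressing on sex, age and principal components removes neither feature.

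Heritability, and its comparison with other populations, belong to Specific Aim 2. Followed as written, the plan would let a paper lean on this result for a statement about the cause of lower PD incidence in Black and African Americans that the data cannot test. It could also leave analysts believing that ascertainment had been dealt with.

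**Working it through.** The protocol gives no target heritability, standard error, European comparator or prevalence for this analysis, so there is no figure to reproduce. The checks below are illustrations.

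**Inputs**

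- Sample case fraction P = 2,000 / 4,000 = 0.5 (Synopsis, at the maximum for both groups).
- Prevalence K = 0.1% (Synopsis, power calculation). All other values of K are assumptions.
- Liability-scale heritability h²_l = 0.20 (assumption).

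**1. Can occurrence halve with heritability unchanged?** Under the liability-threshold model K = 1 − Φ(t).

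- K = 0.1% gives t = 3.090.
- K = 0.05% gives t = 3.291.
- Difference: 3.291 − 3.090 = 0.20 SD.

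A downward shift of 0.20 SD in mean liability therefore halves true occurrence. A shift in the mean changes no variance, so h²_l stays at 0.20. Prevalence stands in for incidence here; the logic is the same.

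**2. What does case-control sampling do to the estimate?** The conversion from the observed 0/1 scale to the liability scale is

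h²_l = h²_o × K²(1−K)² / [φ(t)² P(1−P)].

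At K = 0.1%, φ(3.090) = 0.003367, so the factor is (0.001 × 0.999)² / (0.003367² × 0.25) = 0.352. An observed-scale value of 0.20 / 0.352 = 0.568 therefore corresponds to h²_l = 0.20. Holding 0.568 fixed and changing K:

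| K | factor | h²_l |
|---|---|---|
| 0.05% (assumed) | 0.316 | 0.18 |
| 0.1% (protocol) | 0.352 | 0.20 |
| 0.2% (assumed) | 0.396 | 0.225 |
| 1% (assumed) | 0.552 | 0.31 |

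The factor depends on K and P only. No covariate enters it.

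**3. Simulation check.** True h²_l = 0.20, 1,000 cases and 1,000 controls, 600 markers, four replicates, Haseman-Elston regression. K of 1–2% was chosen for speed. In these three runs sex has no effect on liability.

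| Scenario | observed scale | after sex adjustment | converted with true K | converted with diagnosed K |
|---|---|---|---|---|
| K = 2%, all diagnosed | 0.291 | 0.291 | 0.191 | 0.191 |
| K = 1%, all diagnosed | 0.360 | 0.360 | 0.199 | 0.199 |
| K = 2%, half diagnosed | 0.284 | 0.284 | 0.186 | 0.157 |

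When sex did affect liability, adjustment moved the observed-scale estimates only from 0.290 to 0.273 (K = 2%) and from 0.357 to 0.344 (K = 1%).

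A genuine halving of occurrence (rows 1 and 2) leaves the converted estimate essentially unchanged, so similarity does not point to under-diagnosis. The covariate leaves most of the distortion in place, and the conversion with K and P removes it. In row 3, a K that reflects only diagnosed cases lowers the estimate, so the value used has to be reported.

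**The case against.** **Heritability is secondary and the sentence is hedged.** The primary outcome is novel and known risk factors. No sample size, decision rule or participant procedure depends on heritability, and the text says only that similarity could corroborate an explanation that is probably right. This stands, and it lowers the severity. A reader might take the protocol to assert that similar heritability means under-diagnosis is the sole cause; the wording does not go that far. The inference is still unsupported in its hedged form, because the evidence cannot separate the explanations.

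**The conversion may be in the SAP.** Section 20 already names genetic liability as its target, and the choice of K is the kind of detail an SAP holds. This also stands. A reader might infer that the study will report observed-scale values 1.5 to 2.8 times too high (1/0.655 at an assumed K of 2%, 1/0.352 at 0.1%). That supposes no conversion will be made, which the protocol does not say. What the protocol does say is that covariates do this job, and that is wrong.

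**Sensitivity to K is modest near the protocol's value.** A reader might quote a factor of 1.9 (0.655 / 0.352) or call the European comparison circular. That factor needs K to run from 0.1% to 2%, and the protocol gives only 0.1%. A twofold error either way moves 0.20 to 0.18 or 0.225. The approximate standard error, from √[2/(N²v)] with an assumed relationship variance v = 2×10⁻⁵, is 0.079 on the observed scale at N = 4,000, or 0.079 × 0.352 = 0.028 on the liability scale. The shift is then within one standard error. With v = 4×10⁻⁵ the standard error is 0.020 and the shift is about one standard error. K should be stated and varied, but the comparison is not void.

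**The covariates do some work.** Controls may be patients' partners or public data, so imbalance in sex, age and ancestry is likely, and adjusting for it is sensible. This is a reason to keep the covariates and correct their stated purpose.

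**Conclusion.** The point holds in a limited form. Section 20 attaches an interpretation to the heritability result that the result cannot support, even as hedged. It also gives sex, age and principal components a correction that they do not make, at odds with the purpose it gives them elsewhere.

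On size, a 0.20 SD shift in mean liability is enough to halve occurrence from the protocol's 0.1% with heritability untouched. At P = 0.5 the liability conversion factor is 0.352 at K = 0.1%, and moves by about −10% to +12% for a twofold error in K (0.316 / 0.352 and 0.396 / 0.352). These figures assume the liability-threshold model, equal numbers of cases and controls, and cases and controls otherwise sampled at random. The last assumption is not met: familial cases are included and controls with a family history are excluded. The conversion does not remove that selection, and its size cannot be derived from the protocol.

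Severity is minor to moderate. The single-variant association tests, which serve the primary outcome, are unaffected.

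**What to change.** 1. Delete the sentence linking similar heritability to incidence and diagnosis. State instead that the comparison with European estimates is descriptive, is reported with confidence intervals, and does not address the cause of incidence differences.
2. Reword the purpose of sex, age and principal components in the heritability analysis as population stratification and demographic confounding. State that case-control ascertainment is handled by conversion to the liability scale, using the realised case fraction and a stated K, with a sensitivity range around 0.1% (for example 0.05%, 0.2% and 1%, labelled as assumptions). Report the K used for each population in the European comparison.
3. Add that selection of cases and controls on family history, and the use of public controls, are not removed by this conversion and limit the interpretation.

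An estimator built for case-control samples, such as phenotype-correlation-genotype-correlation regression, is an optional check. The cost is a wording amendment and a few extra lines of output, with no new data and no change to recruitment or to the primary analysis.
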